2.2 Analysis populations

2.2.1 All Enrolled set (AES)

The All Enrolled Set includes all patients enrolled, i.e., all patients who are assigned a study specific patient ID number and for whom informed consent has been obtained (relevant to prospective enrollments only). For the retrospective data collection if the patient has been assigned an ID they will be included in the AES. This population will be used to describe patient flow through the study.

2.2.2 Effectiveness populations

2.2.2.1 Full Analysis Set (FAS)

The FAS will comprise patients in the All Enrolled Set for whom a robotic anastomosis has been performed. A robotic anastomosis is defined as having received at least 1 robotic suture as part of a study procedure. To assist in this determination, for the index procedure, for each anastomosis attempted, the number of robotic sutures will be classified as follows from CRF data:

0 (zero) robotic sutures

≥ 1 robotic sutures (minimum requirement for inclusion in the Safety Analysis Set (SAS) and the FAS)

If the number of robotic sutures is missing, then the anastomosis will be classified as robotic provided the following criteria are met:

The response to the question 'How did you intend to perform the anastomosis?' = 'Robotic **and**

The response to the question "Did you experience any system technical issues resulting in unplanned return to conventional suturing"? = "No".

If at least one anastomosis is classified as robotic (as defined above) the patient will be considered treated robotically and will be included in the FAS for assessment of effectiveness.

The FAS will form the basis of all summarization and analysis of effectiveness variables. However, for each effectiveness variable, the data summary and analysis will only include patients that have non-missing data for the effectiveness outcome being analyzed. The number of patients included in the analysis/summary will be clearly indicated in each tabular presentation.

2.2.2.2 Subpopulations of the FAS.

Two distinct sub-populations will be defined based on the FAS.

- The prospective patient sub-population

Sponsor: MMI Product: Symani system for microsurgical anastomosis Study: PRIMO	
Statistical Analysis Plan Final 22 November 2024	

- The retrospective patient sub-population.

All summaries and analyses will be presented using all data combined and by sub-population.

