Rev. 03
Page: 3/4

	
Immediate and postoperative complications including arterial insufficiency, venous congestion, thrombosis, need for surgical re-exploration of anastomosis, partial flap necrosis or flap loss will be recorded. In the case of lymphatic surgery, the Surgeon will use volumetric measurement to assess the procedure impact on lymphedema.
 
All adverse events will be collected from the procedure date to the study exit of each subject enrolled.

Analysis	
The full analysis set (FAS) is defined as all patients enrolled onto the registry who underwent surgery with Symani. The FAS will be sub-divided into three distinct cohorts, depending on the surgery performed (replantation, free flaps, lymphatic surgery).

Follow-Up Schedule	
Assessments will be made intraoperatively and at regular intervals during hospitalization.
 
The study will be considered complete after all patients have completed their follow-up visits as described in the study protocol.

Inclusion and Exclusion Criteria	
Inclusion criteria
 
1) Male and female patients aged >182) Patients who need a reconstructive procedure and a microsurgical reconstruction is deemed the best option by the plastic, orthopedic or other surgeon in response to a post-oncological, post-traumatic or congenital tissue defect or to treat lymphedema.3) Patients who have been selected by the PI at the Clinical Center as appropriate candidates for treatment with Symani System in accordance with the IFU.4) Subjects who fit the criteria to perform surgery requiring reconstructions using free flaps, replantation, lymphatic reconstructions.5) Subjects who agree to have the surgery and the anaesthesia.6) Subjects who voluntarily decide to participate in this study with the surgery performed with the aid of the Symani System and sign the Informed Consent Form. 
Exclusion criteria
 
1) Subjects who have bleeding or coagulation disorders in the past or present.2) Any criteria that preclude prolonged anesthesia.3) History of anaphylaxis or severe complicated allergy symptoms.

**RASM
POST MARKET CLINICAL FOLLOW-UP
STUDY
Synopsis**

CDC-00031
Rev. 03
Page: 4/4

- 4) Clinically significant cardiovascular, digestive, respiratory, endocrine, or central nervous system disorders or previous mental disorders that may significantly affect the data collection or the ability to comply with the protocol.

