2.1.3.1 Primary effectiveness endpoint – Procedure Robotic Success

Form R or Anastomosis Data Form will be completed for each anastomosis. If the answer to the question 'How did you intend to perform this anastomosis' is 'Robotic' then the anastomosis is included for this endpoint.

The endpoint will be derived for each anastomosis using the question "Did you experience any system technical issues resulting in unplanned return to conventional suturing".

If the response is 'No' and the number of robotic sutures is > 0 or the number of robotic redo sutures is > 0, the anastomosis will be classified as 'intra-operative change from robotic to manual' = 'no'.

If the response is 'yes' anastomosis will be classified as intra-operative change from robotic to manual = 'yes'.

If there is no response to the question the anastomosis classification will be missing.

If the planned approach was manual the result will be N/A

The unit of analysis for this endpoint is the anastomosis.

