2.2.3 Safety populations

2.2.3.1 Safety Analysis Set (SAS)

The SAS will include all patients in the AES that had at least one robotic suture placed or attempted. Note that this definition will include all patients in the FAS as well as any other patients outside of this set (but in the All Enrolled Set) where robotic anastomosis is attempted but no robotic sutures placed. To classify as 'robotic anastomosis attempted' there will be a robotic time recorded on the CRF for at least one anastomosis.

As for the SAS, two sub-populations will be defined based on the SAS.

- The prospective patient sub-population
- The retrospective patient sub-population.

All summaries and analyses will be presented using all data combined and by sub-population.

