2.4.4.1 Analysis of primary effectiveness variable – procedure robotic success

As per section 2.1.3.1 each anastomosis for each patient in the FAS will be assigned to ‘Yes’ or ‘No’ for procedure robotic success. This represents a binary outcome. The analysis of this variable is at the anastomosis level.

For each surgery type (replantation, free flap or lymphatic surgery) stratified frequency tables will be presented stratified by subpopulation (prospective/retrospective) and recipient site/location. The denominator is the number of anastomoses. The proportion of anastomoses classified as a robotic success by stratum and overall for each surgery type will be presented with 95% confidence limits. Results will also be presented on a forest plot.

For replantations a further stratifying variable will be included, namely procedure type (free/nerve).

For each surgery type, a generalized linear mixed model (GLMM) will be used to estimate the percentage of anastomoses classified as robotic success. In SAS, PROC GLIMMIX will be utilized to analyze the data. Subpopulation (prospective/retrospective), recipient site/location and surgeon experience will be included as fixed effects, and surgeon as a random effect. Procedure number (within a surgery type) and anastomosis number (within a procedure) will be included as random terms to acknowledge the dependence in the data (see note above). From the model the adjusted rate of robotic success will be obtained, with 95% confidence limits, for each type of surgery overall and by recipient site/location, by surgeon experience and by subpopulation. (Model 1).

Fixed effects

For free flaps, recipient site will be head and neck, extremities, breast or other.

For lymphatic surgery location will be heads and neck, upper limbs or lower limbs

For replantations there will also be a factor for procedure type (free or nerve), as well as recipient site (as for free flaps) (Model 1a) and results also obtained by procedure type (free/nerve).

For all types of surgery, surgeon experience is classified as microsurgeon, fellow, resident.

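### The primary analysis leaves out patients whose every robotic attempt ended before the first suture, which can only raise the success rate; the size is unknown

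*SAP*

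**What the plan says.** **Who enters.** The protocol synopsis defines the FAS as "all patients enrolled onto the registry who underwent surgery with Symani". SAP 1.5 declares a narrower set, and 2.2.2.1 sets the condition: "A robotic anastomosis is defined as having received at least 1 robotic suture as part of a study procedure". The filter works on patients. With one qualifying anastomosis, "the patient will be considered treated robotically and will be included in the FAS for assessment of effectiveness".

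**Missing suture counts.** Section 2.2.2.1 continues: "If the number of robotic sutures is missing, then the anastomosis will be classified as robotic provided the following criteria are met". The criteria are that robotic suturing was intended and that the answer on technical issues forcing an unplanned return to conventional suturing was 'No'.

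**Where the FAS is used.** "The FAS will form the basis of all summarization and analysis of effectiveness variables". For the primary endpoint, 2.4.4.1 says that "each anastomosis for each patient in the FAS will be assigned to" success or non-success.

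**How the endpoint is scored.** Section 2.1.3.1 selects anastomoses by intent. If the answer on intended method "is 'Robotic' then the anastomosis is included for this endpoint". A technical-issue answer of 'Yes' is a change to manual, with no condition on suture count. An answer of 'No' is favourable if at least one robotic or robotic redo suture was placed.

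**Who is in the safety set.** Section 2.2.3.1 adds patients "where robotic anastomosis is attempted but no robotic sutures placed", identified by a recorded robotic time.

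**The concern.** The endpoint asks whether the surgeon could finish the task with Symani as planned. A patient in whom the robot was tried and given up before a single suture is the clearest negative answer. The SAP foresees such patients and counts them for safety only. Their removal takes failures out of the denominator and never takes out a success.

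The missing-count rule works in the same direction. Take two patients with robotic intent and no suture count on any anastomosis. The one answering 'No' enters the FAS. The one answering 'Yes', a failure under 2.1.3.1, does not. SAP 2.5.6 expects a fair amount of missing data in the retrospective collection, and 1.7 lets those patients count toward the 402.

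What is at stake is the rule in SAP 1.7, under which a lower 95% limit above 85% supports a claim of superiority over manual surgery. No analysis of all robotic attempts is planned beside the FAS analysis.

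**Working it through.** **Inputs from SAP 1.7.** Reference rate 85%, n = 402, exact 95% limits, pass if the lower limit exceeds 85%. The number of anastomoses per patient is stated to be unknown. The documents give no rate of pre-suture abandonment, so that is an assumed range below.

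**Step 1: the plan's own rule.** With a two-sided exact 95% interval, the smallest passing count at n = 402 is 356. If true success is 85%, P(X ≥ 356) = 2.4%. At 89% the same rule has power 64.9% (75.6% if the limit is one-sided), not the stated 85%. That shortfall is a separate matter; only the 2.4% is used here.

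**Step 2: which attempts are lost.** Reading 2.2.2.1 with 2.1.3.1, for an anastomosis intended as robotic:

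| Suture count | Technical-issue answer | Another anastomosis in the patient qualifies | No other qualifies |
|---|---|---|---|
| 0 | Yes | in, failure | patient out |
| 0 (and no redo suture) | No | no class in 2.1.3.1, so dropped under 2.5.2 | patient out |
| missing | Yes | in, failure | patient out |
| missing | No | in, but the class is unclear because a count above 0 is required | patient in, same unclear class |

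The right-hand column is where failures leave the analysis through the FAS.

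**Step 3: effect on the rate.** Let p be true success over all intended-robotic attempts and e the share of attempts that are failures lost this way. The rate in the FAS is p/(1 − e). With p = 0.85:

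- e = 1%: 0.85/0.99 = 85.9%
- e = 2%: 0.85/0.98 = 86.7%
- e = 3%: 0.85/0.97 = 87.6%

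**Step 4: effect on the decision.** Assume 402 independent attempts, one per patient. The number analysed is n ~ Bin(402, 1 − e). Given n, successes are Bin(n, p/(1 − e)), and the rule passes when they reach the smallest count whose exact lower limit exceeds 85%. Averaging over n:

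| e | chance of wrongly passing |
|---|---|
| 0 | 2.4% |
| 1% | 5.7% |
| 2% | 14.3% |
| 3% | 29.0% |

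The binomial is discrete, so fixing n at one value moves these figures a little. At e = 2% with n fixed at 394 the result is 15.7%.

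**Step 5: one illustrative dataset.** 352/402 = 87.6%, lower limit 83.9%, does not pass. With 8 pre-suture failures left out, 352/394 = 89.3%, lower limit 85.9%, passes. Losing 5 is enough: 352/397 has lower limit 85.1%.

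**Step 6: several anastomoses per patient.** Suppose each patient has m anastomoses, each failing before the first suture independently with probability q and answered 'Yes'. A patient is lost only if all m fail, so the share lost is q^m. For m = 2 and q = 2%, that is 0.02² = 0.04%, and the rate becomes 0.85/0.9996 = 85.03%. For 402 × 2 = 804 anastomoses the passing count is 704. The chance of wrongly passing is 2.2% with nothing lost and 2.3% with this loss. If instead a system failure ends all robotic use in a patient, the m failures occur together, e returns to q, and the inflation in Step 3 applies in full.

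**The case against.** A reader might infer that every attempt failing before the first suture is removed from the endpoint. The documents do not support that. The FAS admits patients, not anastomoses, and 2.1.3.1 then takes every intended-robotic anastomosis of an admitted patient and scores 'Yes' as a change to manual whatever the suture count. SAP 1.7 and section 2 expect patients with more than one anastomosis, and Step 6 shows how little is lost if failures are then independent.

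A reader might also infer that the missing-count rule drops failures and keeps successes throughout. It decides FAS membership only. Within a FAS patient, a missing count with 'Yes' is still a failure, and a missing count with 'No' does not clearly meet the favourable class either.

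Two further points are fair. The narrowing is declared in 1.5, and patient flow is reported for the All Enrolled Set, so nothing is hidden. And 2.4.4.1 produces rates by surgery type from a mixed model, while the pooled 85% rule stands only in 1.7; the figures above follow 1.7.

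What remains is the patient with no qualifying anastomosis. Declaring the narrower set does not undo the loss of that failure. Patients with a single attempt are exposed to it fully, as are patients in whom a system failure stops robotic use before any suture. The documents give no figures that would make this group negligible.

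**Conclusion.** The point holds in this limited form. The FAS leaves out patients with no qualifying robotic anastomosis, and among them are outright failures of the primary endpoint. For patients whose suture counts are all missing, entry depends on the answer that scores the endpoint. The direction of this loss is certain: it can only raise the success rate, by about 0.9 percentage points near 85% for each 1% of attempts lost. The size cannot be found from the documents. The rise in false-pass risk from 2.4% to about 6%, 14% and 29% rests on one independent attempt per patient, true success of exactly 85% and an assumed loss of 1% to 3%. It shrinks to almost nothing with two independent anastomoses per patient, and the upward shift in the rate returns in full if failures cluster within patients. Because the exclusion acts directly on a superiority claim and the correction needs no new data items, it should be made before the primary analysis is run.

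**What to change.** 1. Run the primary endpoint on every anastomosis intended as robotic, in every patient in whom Symani was used or attempted. That is the Safety Analysis Set of 2.2.3.1, plus any patient with robotic intent and a technical-issue answer of 'Yes'. This avoids bringing in operated patients in whom Symani played no part.
2. Score an anastomosis as a failure if the technical-issue answer is 'Yes', or if no robotic suture was placed, whether at first attempt or redo. This also closes the gap in 2.1.3.1 for 'No' with zero sutures.
3. Do not let the technical-issue answer decide entry when the suture count is missing. Score 'Yes' as failure. For 'No', state one scoring rule in advance and test the other in a sensitivity analysis.
4. Remove from 2.2.2.1 the statement that one robotic suture is the minimum for the SAS as well. It contradicts 2.2.3.1.
5. Keep the present FAS as a sensitivity analysis, and report how many patients and anastomoses separate the two sets.

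Cost: SAP wording and programming. Intent, suture counts, robotic time and the technical-issue answer are already on the case report forms. The reported success rate may be less favourable.

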2.2.3 Safety populations

2.2.3.1 Safety Analysis Set (SAS)

The SAS will include all patients in the AES that had at least one robotic suture placed or attempted. Note that this definition will include all patients in the FAS as well as any other patients outside of this set (but in the All Enrolled Set) where robotic anastomosis is attempted but no robotic sutures placed. To classify as 'robotic anastomosis attempted' there will be a robotic time recorded on the CRF for at least one anastomosis.

As for the SAS, two sub-populations will be defined based on the SAS.

- The prospective patient sub-population
- The retrospective patient sub-population.

All summaries and analyses will be presented using all data combined and by sub-population.

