1.5 Modifications from the statistical section of the protocol

Modification to the definition of the FAS to only include patients who had at least one robotic suture placed.

Definition of a safety set to be all patients with at least one robotic suture attempted.

Amendment to the sample size section to note analysis at the anastomosis level and to remove notes about missing data as this is handled under data derivations.

Amendment to the sample size section to note that the total sample specified in the PRIMO study protocol can be achieved through prospective or retrospective patients. That is, the data of retrospective patients is now included in the target sample size.

Amendment to the analysis of the primary effectiveness endpoint to be at the anastomosis level rather than at the patient level.

Amendment to the analysis of anastomosis time to use a mixed model rather than a KM analysis. This change has been made since all anastomoses will have a time, so a specific 'time to event' analysis (eg KM) is not needed as there are no censored times. Using a mixed model will allow adjustment for the dependence in the data.

Definition of some additional efficacy endpoints namely:

- Free flap viability at 30 days
- Intra-operative anastomosis patency

Definition of some additional safety endpoints namely:

- Freedom from device related serious adverse events prior to discharge

Sponsor: MMI Product: Symani system for microsurgical anastomosis Study: PRIMO	
Statistical Analysis Plan Final 22 November 2024	

- Freedom from device related adverse events prior to discharge
- All cause re-admission rates
- All cause re-operation rates up to 30 days
- All cause mortality rates up to 30 days

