2.5.6 Statistical technical issues

The models noted in the efficacy analyses propose a default covariance structure of type=VC, which is a simple diagonal matrix with equal variances across all levels of the surgeon ID variable. This will be examined to determine if the structure is appropriate, or whether an alternative structure is more appropriate. The use of the GROUP= option in the random statement may also be investigated if type=VC does not adequately explain the variance observed across surgeons (that is, including GROUP=surgeon in the random statement). This will be done as part of normal model checking procedures and described as part of the reported statistical analysis results.

The retrospective data collection may have a reasonable amount of missing data. All data available will be used as much as possible and the derivation of the effectiveness endpoints defines how to obtain a result if possible. All data summaries will clearly indicate the amount of missing data.

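### For a patient with no robotic suture, the safety set counts an attempt only if a robotic time was recorded, so a reported system failure without a time falls outside every safety table

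*SAP*

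**What the plan says.** SAP 2.2.3.1 puts in the safety set "all patients in the AES that had at least one robotic suture placed or attempted". It says that this takes in the whole FAS plus enrolled patients "where robotic anastomosis is attempted but no robotic sutures placed". For that second group it gives one operational test: "there will be a robotic time recorded on the CRF for at least one anastomosis". There is no alternative and no fallback for a missing time.

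Two other places describe the same set differently:

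- SAP 1.5 has no time condition: "Definition of a safety set to be all patients with at least one robotic suture attempted".
- SAP 2.2.2.1 is stricter. It labels one or more robotic sutures as the "minimum requirement for inclusion in the Safety Analysis Set (SAS) and the FAS".

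SAP 2.2.2.1 also has a fallback for the FAS: "If the number of robotic sutures is missing, then the anastomosis will be classified as robotic provided the following criteria are met". The criteria are robotic intent and a 'No' to the technical-issue question.

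The form for each anastomosis (SAP 2.1.3.1) already records the intended approach and whether there was a system technical issue "resulting in unplanned return to conventional suturing". The safety-set rule uses neither item.

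**The concern.** A time field is an indirect marker of an attempt. SAP 2.1.2 describes it as an execution time and SAP 2.1.3.2.2 as a usage time. Neither says what is entered when the system fails before the first stitch, or whether a recorded zero counts as a time. The field can also simply be blank, and SAP 2.5.6 warns: "The retrospective data collection may have a reasonable amount of missing data".

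The item that directly reports a device failure is collected but plays no part in the test. Where a time is absent, the rule can therefore remove patients because the device failed, from the set meant to describe device safety. SAP 2.4.6 uses that set for the adverse event tables (including device deficiencies), freedom from device-related serious and non-serious events, re-admission, re-operation and length of stay. SAP 2.1.5.1.1 adds a supporting analysis that counts unclassifiable patients as not event-free. It cannot help here, because these patients are not in the set to begin with.

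**Working it through.** The plan gives no figure on this point, so there is none to reproduce. The check has two parts.

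**1. Routes into the safety set (SAP 2.2.2.1 and 2.2.3.1)**

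| Record across all of a patient's anastomoses | FAS | Safety set |
|---|---|---|
| At least one robotic suture on any anastomosis | in | in, through the FAS |
| Suture count missing, intent robotic, technical issue 'No' on any anastomosis | in | in, through the FAS |
| No robotic suture, robotic time on any anastomosis | out | in, by the time test |
| Intent robotic, technical issue 'Yes', sutures zero or missing, no robotic time on any anastomosis | out | out |

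The last row is the gap. The FAS fallback cannot close it, because it requires the technical-issue answer to be 'No'. Such a patient stays only in the All Enrolled Set, which SAP 2.2.1 uses for patient flow. By contrast, the derivation in SAP 2.1.3.1 classifies an anastomosis with robotic intent and technical issue 'Yes' as a change from robotic to manual, with no suture or time condition.

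**2. Possible size**

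Inputs: N = 402 patients, the planned minimum in SAP 1.7. The number excluded, k, is not in the documents and is assumed to be 1 to 20. Let x be the number of patients with a device-related event among those kept, and e the number among those excluded.

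- Rate as the SAP would report it: x/(402 − k)
- Rate with the excluded patients restored: (x + e)/402
- Limits: exact (Clopper-Pearson) 95%

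The reported rate is too low whenever e/k exceeds x/(402 − k).

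With k = 4:

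| x | e | Reported rate (upper limit) | Restored rate (upper limit) |
|---|---|---|---|
| 4 | 0 | 4/398 = 1.01% (2.55%) | 4/402 = 1.00% (2.53%) |
| 0 | 2 | 0/398 = 0% (0.92%) | 2/402 = 0.50% (1.79%) |
| 4 | 4 | 4/398 = 1.01% (2.55%) | 8/402 = 1.99% (3.88%) |
| 0 | 4 | 0/398 = 0% (0.92%) | 4/402 = 1.00% (2.53%) |

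The last row, expressed as freedom from events:

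- Reported: 398/398 = 100%, lower limit 0.025^(1/398) = 99.1%.
- Restored: 398/402 = 99.0%, lower limit 100 − 2.53 = about 97.5%.

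The same extreme (x = 0, e = k) over the assumed range:

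| k | Reported (upper limit) | Restored (upper limit) |
|---|---|---|
| 1 | 0/401 (0.92%) | 1/402 = 0.25% (1.38%) |
| 4 | 0/398 (0.92%) | 4/402 = 1.00% (2.53%) |
| 12 | 0/390 (0.94%) | 12/402 = 2.99% (5.16%) |
| 20 | 0/382 (0.96%) | 20/402 = 4.98% (7.58%) |

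Over this range the understatement runs from essentially nothing to about 5 percentage points.

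**The case against.** The case against has several parts, and most of it stands as a limit on the point.

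- **The group is narrow.** One robotic suture or one robotic time on any anastomosis keeps the patient in. A missing time does no harm where a robotic suture was placed, or where the FAS fallback applies.
- **Early failure need not mean no time.** A reader might infer that a malfunction before the first stitch usually leaves the time blank. The documents do not say so, and a usage time could be logged once the system is engaged.
- **Early failure need not mean harm.** A reader might infer that those excluded are the patients most harmed. The documents do not support that: a failure before any stitch may involve little exposure. Exclusion is tied to device failure, but not demonstrably to adverse events.
- **The events need not vanish.** SAP 2.4.6.1 lists all adverse event data and states no restriction to the safety set, and SAP 2.3 reports disposition on the All Enrolled Set. What is lost is their place in the tables and rates.
- **The safety-set rule is not independent of the FAS.** A reader might infer that widening the FAS to robotic intent would leave the gap open. It would not, because SAP 2.2.3.1 includes every FAS patient.

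None of this removes the gap. With the FAS as defined, a reported device failure without a suture or a time has no route into the safety set.

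**Conclusion.** The point holds as a gap in a stated rule. SAP 2.2.3.1 sets out to include attempted robotic sutures, but its only test for a patient with no robotic suture can miss a failure that the form itself records. Three sections of the SAP also describe the safety set in three different ways.

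The size is unknown and may be zero. With 4 of 402 affected, an assumption, the effect runs from negligible to a reported 100% freedom from device-related events where 99.0% is correct. The upper end requires every excluded patient, and nobody else, to have an event. The direction is the reason to act: if the excluded failures carry events more often than the other patients do, the bias favours the device. The change is worth making because it is cheap, not because a large distortion has been shown.

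**What to change.** In SAP 2.2.3.1, define a robotic anastomosis as attempted when at least one anastomosis has either:

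- an intended approach of 'Robotic' together with 'Yes' to the technical-issue question, or
- a recorded robotic time (and say whether a time of zero counts).

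Use robotic intent alone only as a sensitivity set. As the main rule it would admit patients in whom the system was never engaged, which would dilute the device-related rates. As a sensitivity set it also reaches patients whose technical-issue answer, suture count and time are all missing.

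Reconcile the note in SAP 2.2.2.1 that makes one robotic suture the minimum for the safety set with SAP 1.5 and 2.2.3.1. Report how many patients enter through each route.

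The cost is a sentence or two in the SAP and one extra sensitivity run. Both items are already collected for each anastomosis. The downside is that a few patients with little device exposure may enter the safety set.
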